11.3 Power and Sample Size

Up to 28 subjects will be enrolled on this pilot study to assure retention of at least 24 complete, evaluable subjects for the primary endpoint. The expected accrual rate is four per month with accrual lasting approximately six months. Participants will be randomized equally (n=12 per group) to standard of care or KeraStat Cream. With 12 participants in each treatment group expected to complete the study, we will be able to calculate a 95% confidence interval around the compliance rate in each group with a

maximum total confidence interval width of 0.578 (this maximum occurs if the compliance proportion is 0.5).

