3.3 Inclusion of Women and Minorities

Men and women of all races and ethnicities who meet the above-described eligibility criteria are eligible to participate in this study. The study consent form will also be provided in Spanish for Spanish-speaking participants.

Based on WFBCCC population estimates, we may expect approximately 20% of participants to be women. Translating this to our sample size estimate of 22 patients, we may enroll approximately 4-5 women. We may enroll approximately 10-13% Black or African American patients. Based on our catchment area and hospital demographics we do not expect high accruals of individuals of Hispanic/Latino, American Indian/Alaska Native or Asian ancestry; however, no individual will be excluded from the study if they satisfy the above inclusion/exclusion criteria. Should we not meet or exceed these estimates, the PI will engage the Office of Cancer Health Equity to discuss strategies to enhance recruitment in these target populations.

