6.0 Treatment Plan

6.1 Study Design

This is a single site, randomized, open-label comparison pilot study to assess the feasibility and effectiveness of KeraStat Cream in managing RT EASR in patients undergoing RT to the head and neck. Sufficient subjects will be screened such that 24 total subjects will complete the study. Patient compliance is expected to be good, so a target recruitment of 28 subjects is anticipated. Patients will be screened for inclusion at their consultation visit in the WFBCCC Department of Radiation Oncology. A total of 28 head and neck cancer patients to receive definitive RT will be recruited and consented.

After informed consent, the patient will be registered to the study and randomized to either routine skin care (RSC) or KeraStat study arms. Patients randomized to the KeraStat arm will be provided with KeraStat Skin Cream for application as often as needed but at least twice daily, morning and evening. Baseline pre-RT assessments will be completed prior to the initiation of RT. These can be completed on the date of RT treatment planning CT simulation scan or later during the radiation treatment-planning process (generally 1.5-2 weeks).

Patients are generally treated with RT using daily fractions delivered Monday through Friday, with weekends and holidays off, for approximately 6-7 weeks. Generally, radiation treatment breaks should be avoided whenever possible, but treatment breaks deemed necessary by the treating radiation oncologist are acceptable and will be recorded, as will the indication for the treatment break. While on treatment, patients are seen by the radiation oncologist (and possibly other support staff including but not limited to nurses, speech language pathologists, dieticians, navigators and case workers) once weekly as part of a routine on-treatment visit. The purpose of this visit is to review the patient's treatment course, monitor for expected and unexpected toxicity, and manage the patient appropriately.

Patients who receive definitive RT receive chemotherapy. Cisplatin is preferred if medically possible, with other cytotoxic regimens acceptable at the discretion of the medical oncologist. Anti-EGFR antibody therapy (i.e. cetuximab) is not permitted.

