6.2 Treatment Administration

Beginning on the first day of RT, patients will be instructed to apply skin care according to their randomization arm (Section 6.2.1). The patient will be instructed to apply the assigned agent every day as needed, but at least twice daily, to the skin of the head and neck within the region of interest.

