11.0 Statistical Considerations

11.1 Analysis of Primary Objective

The completion rate will be used as a measure of feasibility, with participants with an average of 10 or more applications per week being classified as compliant. In each arm, a 95% confidence interval will be calculated around the estimate of compliance.

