11.2 Analysis of Secondary Objective

- 11.2.1 The rate of discontinuation for any reason will be used as a measure of tolerability, with patients who do not discontinue the skin care regimen being classified as tolerant. In each arm, a 95% confidence interval will be calculated around the estimate of tolerability.
- 11.2.2 Proportion of EASR (CTCAE v5.0 Grade 2+ radiation dermatitis) will be compared between the KeraStat group and the RSC group at the end of treatment, using a Fisher's exact test.
- 11.2.3 Mean scores of the modified PRO-CTCAE patient-reported outcome scales collected each week over the 6-7 weeks of radiation therapy and at the onemonth post treatment follow-up visit will be compared between the KeraStat and RSC groups using a simple repeated measures analysis of variance model with treatment group as the independent variable of interest.
- 11.2.4 Mean DLQI score at each time point will be compared between the KeraStat and RSC groups, again using a simple repeated measures analysis of variance model with treatment group as the key independent variable. Additionally, the mean of the highest DLQI score across all time points will be compared between the KeraStat and RSC groups using a t-test.
- 11.2.5 Skin coverage (calculated as number of tubes of KeraStat Cream used per week) will be summarized with a frequency distribution and computation of central tendency and variability (mean, median, and standard deviation).

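### Section 11.3 sizes the primary compliance rate on 12 completers per arm and Section 11.1 names no denominator, so patients who withdraw can fall out of the feasibility estimate

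*Combined protocol and SAP*

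**What the plan says.** Section 11.3 allows up to 28 enrolments "to assure retention of at least 24 complete, evaluable subjects for the primary endpoint". Its precision statement starts from completers: "With 12 participants in each treatment group expected to complete the study", the 95% interval for compliance in each group is at most 0.578 wide. The same paragraph gives the completer number as the number randomised: "Participants will be randomized equally (n=12 per group) to standard of care or KeraStat Cream". That makes 24, not 28. Section 6.1 repeats the completer target, "Sufficient subjects will be screened such that 24 total subjects will complete the study", with recruitment of 28. Section 3.3 uses a third figure for its demographic projection: "Translating this to our sample size estimate of 22 patients".

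The primary analysis is in Section 11.1. It calls the measure a completion rate, "with participants with an average of 10 or more applications per week being classified as compliant", and asks for a 95% interval in each arm. It names no denominator, no weeks over which the average is taken, and no handling of withdrawals or missing forms. The term evaluable is not defined anywhere. Section 5.1 says only that feasibility is compliance with the directions for use.

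Tolerability in Section 11.2.1 is a separate per-arm rate, with "patients who do not discontinue the skin care regimen being classified as tolerant". It names no denominator either.

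**The concern.** Withdrawal bears directly on whether a skin care regimen is feasible. Section 6.4 stops the cream for intolerance or related adverse events, and Section 6.6 lets patients leave for several reasons, so some departures may themselves be failures of feasibility. If the analyst takes the set on which Section 11.3 is sized, those patients leave both numerator and denominator.

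The undefined averaging window is a second route to the same effect. Appendix G records applications in the last week at each visit. If a patient leaves the study and only the reported weeks are averaged, a short spell of good use counts as full compliance. Section 6.6 lists the stopping of RT as a reason for removal, and the footnote to the Section 7.2 calendar ends weekly visits when treatment stops, so such departures are foreseen.

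This is the only primary endpoint of a pilot whose data are meant to inform later randomised studies (Section 1.0). Two analysts could follow the text in good faith and report different primary results.

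**Working it through.** **Inputs.** From Section 11.3: up to 28 enrolled, 24 complete and evaluable, 12 per group, maximum width 0.578 at a proportion of 0.5. From Section 11.1: a cut-off of 10 applications per week and a 95% interval per arm, method not named. From Section 6.1: RT lasting about 6 to 7 weeks and at least two applications daily, which is 14 per week.

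**The plan's own figure.** The exact (Clopper-Pearson) 95% interval for 6/12 is 0.211 to 0.789, width 0.578. This is also the maximum over all counts for n = 12. Other methods at 6/12 give 0.566 (Wald), 0.649 (Wald with continuity correction) and 0.492 (Wilson). The stated figure is therefore correct, exact, and computed on completers. For 14 per arm the maximum exact width is 0.539 (7/14: 0.230 to 0.770).

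**Effect of the denominator.** Assumptions: 28 enrolled and randomised 1:1, so 14 per arm, with the implied loss of 28 - 24 = 4 split 2 and 2. If k completers comply and c of the 2 lost patients would have met the cut-off, the gap is k/12 - (k + c)/14. With c = 0 this equals k/84.

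| k | k/12 (95% CI) | k/14 (95% CI) | Gap, points |
|---|---|---|---|
| 6 | 50.0% (21.1 to 78.9) | 42.9% (17.7 to 71.1) | 7.1 |
| 9 | 75.0% (42.8 to 94.5) | 64.3% (35.1 to 87.2) | 10.7 |
| 10 | 83.3% (51.6 to 97.9) | 71.4% (41.9 to 91.6) | 11.9 |
| 12 | 100% (73.5 to 100) | 85.7% (57.2 to 98.2) | 14.3 |

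At k = 10 the gap depends on c:
- c = 1: 83.3% - 11/14 (78.6%) = 4.8 points.
- c = 2: 83.3% - 12/14 (85.7%) = -2.4 points, so completers-only understates.

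If all 4 losses fell in one arm, 9/10 = 90.0% would compare with 9/14 = 64.3%, a gap of 25.7 points.

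**Effect of the averaging window.** A twice-daily user who leaves the study after w weeks averages 14.0 over reported weeks, whatever w is. Over all RT weeks the average is 14w/6 or 14w/7:
- w = 1: 2.3 or 2.0
- w = 2: 4.7 or 4.0
- w = 3: 7.0 or 6.0
- w = 4: 9.3 or 8.0
- w = 5: 11.7 or 10.0

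The two methods disagree for departures after weeks 1 to 4. From week 5 they agree that the patient is compliant.

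A user who stops the cream after 3 weeks but stays on study is already caught, because Appendix G continues weekly: 42/6 = 7.0, 42/7 = 6.0, or 42/8 = 5.25 (7 RT forms plus the 1-month form).

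**The case against.** The strongest reply is that Section 11.1 does not order a completers-only analysis. Sizing on the number expected to remain is ordinary planning and does not by itself define an analysis set. Section 11.1 speaks of participants and of a completion rate, which read literally needs non-completers in its denominator. This stands as far as it goes: a reader might infer that the plan excludes withdrawals, and the documents do not say so. But Section 11.1 then defines the rate by application frequency, so the term does not settle the denominator. Section 11.3 ties the primary endpoint by name to complete, evaluable subjects, and nothing elsewhere supplies another set.

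A second reply is that attrition is not hidden. Section 11.2.1 reports discontinuation, Section 6.6 requires withdrawal reasons to be recorded, and Section 7.1.3 has patients who terminate early seen by study staff. All true, but a separate discontinuation rate does not correct the primary rate.

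A third reply is that a patient whose RT is stopped may have followed directions for as long as they applied, so dividing by the full course is a choice of estimand and not the repair of an error. This is right. It is also right that not every withdrawal is a failure: the user who leaves after week 5 meets the cut-off even over the full course. A blanket rule that scores all withdrawals as non-compliant would go too far.

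**Conclusion.** The gap is real and worth closing. The only text on who counts for the primary endpoint points to completers, and that basis tends to overstate compliance. With 14 randomised and 2 lost per arm, all losses non-compliant, the overstatement runs from 7.1 points (6 compliant) to 14.3 points (12 compliant). It shrinks or reverses if the lost patients were using the cream as directed. Full enrolment, the 2 and 2 split and the compliance of those lost are assumptions, not statements in the plan.

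Three stronger readings are not supported:
- That 0.578 is wrong. It is the correct exact width for 12.
- That a go or no-go decision would change. No feasibility threshold is stated, and the shift lies inside wide intervals.
- That Section 9.5 flatly contradicts Section 6.4 and Appendix J on how long the cream is applied. Section 9.5 describes use during RT and does not say that use ends there; the other two run to about 1 month after RT. The wording should be aligned, and this point takes no position on what it should say.

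**What to change.** In Section 11.1:
- Make all randomised participants in each arm the primary denominator.
- Apply the cut-off of 10 per week to the average over the patient's scheduled Appendix G weeks during RT. Count weeks after withdrawal from the study or discontinuation of the agent as zero.
- Count participants with no application data as non-compliant, but add no rule that every withdrawal is non-compliant.
- Where single forms are missing while the patient is still on the agent, average over the available weeks, with a zero-imputed sensitivity analysis.
- As further sensitivity analyses, report the completers-only rate and a version that sets aside patients who never started RT, or averages only to the end of RT when RT is stopped early. This version is needed because randomisation precedes RT while application does not: "Beginning on the first day of RT, patients will be instructed to apply skin care according to their randomization arm".

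Use the same all-randomised set in Section 11.2.1. In Section 11.3, reconcile the 12 per group randomised with up to 28 enrolled, name the exact interval, and state its maximum width for the number randomised per arm (0.539 if 14, 0.578 if 12). The 22 in Section 3.3 can be brought into line at the same time, though nothing here depends on it. Align the wording on duration of application in Sections 6.4 and 9.5 and Appendix J.

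The change needs no extra patients or forms. The reported rate may be lower. The interval is slightly wider at high compliance (10/12: 0.463; 10/14: 0.497) and narrower near one half (6/12: 0.578; 6/14: 0.535). The primary rule also scores patients who never start RT as non-compliant with an agent they were not yet due to use, which is why the last sensitivity analysis should be reported beside it.

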11.4 Estimated Accrual Rate

At the Wake Forest Baptist Comprehensive Cancer Center, we see approximately 320 new cases of pharyngeal, oral cavity and laryngeal cancers per year. Internal metrics within the Radiation Oncology Department have identified an average rate of 6.4 new patients starts over the last 3 years. This has increased to 8.3 new patient starts per month over the last 9 months (January-August 2019). As such, we expect a patient accrual rate of approximately 4 patients per month.

Appendix A - Eligibility Checklist

IRB Protocol No. IRB00062012 WFBCCC Prot	ocol No. 9	7319		
Study Title: Pilot Study of KeraStat Cream for Radiation Dermatitis during Head and Neck Radiotherapy				
Principal Investigator: [name]				
Inclusion Criteria (as outlined in study protocol)	Criteria is met	Criteria is NOT met	(Plea	Source Used to Confirm * ase document dates and lab results)
Diagnosis of head and neck cancer planned to receive conventionally-fractionated definitive radiotherapy to the head and neck to a total prescribed dose of at least 60 Gy				
Able and willing to sign protocol consent form				
Able and willing to complete tolerability and quality of life assessments				
Able and willing to have photographs of the affected area taken regularly				
Exclusion Criteria (as outlined in study protocol)	Criteria NOT present	Criteria is present	(Plea	Source Used to Confirm * ase document dates and lab results)
Women who are pregnant, lactating/nursing or plan to become pregnant				
Previous radiation therapy to the area to be treated with radiation therapy				
Active, medically necessary use of topical corticosteroids in the irradiation area				
Active scleroderma or lupus requiring systemic medication				
Treatment with anti-EGFR antibodies for head and neck cancer (previously or planned)				
This subject is eligible / ineligible for participation in this study.				

Signature	of research	n professional o	confirming eligibili	ty:	
Date:	/	/			
Signature	of Treating	, Physician:			
Date:	/	/			
Signature	of Principa	ıl Investigator**	*. 		
Date:	/	1			

^{*} Examples of source documents include clinic note, pathology report, laboratory results, etc. When listing the source, specifically state which document in the medical record was used to assess eligibility. Also include the date on the document. Example: "Pathology report, 01/01/14" or "Clinic note, 01/01/14"

^{**}Principal Investigator signature can be obtained following registration if needed

Appendix B – Protocol Registration Form

DEMOGRAPHICS	
Patient: Last Name:	First Name:
MRN:	DOB (mm/dd/yy): / / /
ZIPCODE:	En
SEX: ☐ Male ☐ Female	Ethnicity (choose ☐ Hispanic one): ☐ Non-Hispanic
Race (choose all that ☐ WHITE ☐	BLACK □ ASIAN
apply): □ PACIFIC ISLAN	IDER ☐ NATIVE AMERICAN
Height: inches	Weight:lbs.(actual)
Surface Area:m²	
Primary Diagnosis:	
Date of Diagnosis: / /	
Performance Status: ECOG	
PROTOCOL INFORMATION	
Date of Registration:	//
MD Name (last) :	
Date protocol treatment started:	
Informed written consent:	□ YES □ NO
(consent must be signed prior to	
registration)	
Date Consent Signed:	/
PID # (to be assigned by OnCore):	

Protocol Registrar can be contact by calling [contact] between 8:30 AM and 4:00 PM, Monday – Friday.

Compete the eligibility checklist in WISER and then give the completed Eligibility Checklist and Protocol Registration Form must be hand delivered, faxed or e-mailed to the registrar at [contact] or [contact], respectively.

Appendix C - Race & Ethnicity Verification Form

Thank you so much for helping us to verify your race and ethnicity to ensure the quality of our information. As a brief reminder, the information you provide today will be kept confidential.

1.	Are you: Hispanic or Latino/a Not Hispanic or Latino/a
2.	What is your race? One or more categories may be selected. White or Caucasian Black or African American American Indian or Alaskan Native Asian Native Hawaiian or Other Pacific Islander Other, Please Specify:
Internal	use only:
Name:	MRN#:
	self-reported race and ethnicity of the participant verified at the time of consent? S No
	screpancy found? Yes No No Ces, please provide what is currently indicated in the EMR: Ethnicity: Race:
Additiona	I comments:

Appendix D – Demographic and Health Behaviors

Form should be given to the participant to complete.

The following questions will ask about your demographic background and your health behaviors. There are no "right" or "wrong "answers to these questions. The information you provide will remain strictly confidential.

1.		confident are you filling out medical forms by yourself?
		Extremely
		Quite a bit
		Somewhat
		A little bit
		Not at all
2.	What	is your ethnicity?
		Hispanic or Latino
		Not Hispanic or Latino
3.	What	is your race? One or more categories may be selected. Mark all that apply.
		White
		Black or African American
		American Indian or Alaskan Native
		Asian
		Native Hawaiian or other Pacific Islander
		Other → Please specify:
		Prefer not to answer
4.	What	is your current marital status?
		Married
		Living as married
		Divorced
		Widowed
		Separated
		Single, never been married
		Prefer not to answer

Pilot Study of KeraStat® Cream for Radiation Dermatitis during Head and Neck Radiotherapy

Wake Forest Baptist Comprehensive Cancer Center WFBCCC 97319

5.	What is the highest grade or level of schooling you completed?
	□ Less than 8 years
	□ 8 through 11 years
	□ 12 years or completed high school
	 Post high school training other than college (vocational or technical)
	□ Some college
	□ College graduate
	□ Postgraduate
	□ Prefer not to answer
3.	During the past 4 weeks, did you have enough money to meet the daily needs of your family?
	□ Yes
	□ No

Section 2: The next section will ask you some questions about your physical activity.

Physical activities are activities where you move and increase your heart rate above its resting rate, whether you do it for pleasure, work or transportation. The following questions ask about the amount and intensity of physical activity you usually do. The intensity of an activity is related to the amount of energy you use to do these activities.

Examples of physical activity intensity levels:

Light activities · your heart beats slightly faster than normal . you can talk and sing Stretching Walking Vacuuming or Light Yard Work Leisurely Moderate activities · your heart beats faster than normal · you can talk but not Aerobics Swimming sina Fast Strenath Training Walking Gently Vigorous activities your heart rate increases a lot · you can't talk or your talking is broken up by Tennis, Racquetball, Jogging Pickleball or Badminton large breaths Stair Running Machine

7. How physically active are you? (check one answer on each line)

	Does this accurately describe you?	
a) I rarely or never do any physical activities.	Yes	No
 b) I do some light or moderate physical activities, but not every week. 	Yes	No
c) I do some light physical activity every week.	Yes	No
d) I do moderate physical activities every week, but less than 30 minutes a day or 5 days a week.	Yes	No
e) I do vigorous physical activities every week, but less than 20 minutes a day or 3 days a week.	Yes	No
f) I do 30 minutes or more a day of moderate physical activities, 5 or more days a week.	Yes	No
g) I do 20 minutes or more a day of vigorous physical activities, 3 or more days a week.	Yes	No

Section 3: This section will ask you some questions about smoking. For the questions below, please try to select a single number.

ntire life?

9. How many total years have you smoked (or did you smoke) cigarettes? Do not

WFBCCC 97319

count any time you may have stayed off cigarettes Years
10. On average when you have smoked, about how many cigarettes do you (or did you) smoke a day? A pack usually has 20 cigarettes in it. Number of cigarettes per day
11. How long has it been since you last smoked a cigarette (even one or two puffs)? First check which one of the following choices applies to you. Then, if applicable, write a number on the line for how many days, weeks, months, or years it has been since your last cigarette.
□ I smoked a cigarette today (at least one puff). □ 1-7 days. Number of days since last cigarette: □ Less than 1 month Number of weeks since last cigarette: □ Less than 1 year Number of months since last cigarette: □ More than 1 year Number of years since last cigarette: □ Don't know / Don't remember.
12. Which of the following phrases best characterizes you at this time? (Please mark only one response.)
 □ Normal, no complaints, no symptoms of disease □ Able to carry on normal activity, minor symptoms of disease □ Normal activity with effort, some symptoms of disease □ Care for self, unable to carry on normal activity or to do active work □ Require occasional assistance but able to care for most of personal needs □ Require considerable assistance for personal care □ Disabled, require special care and assistance □ Severely disabled, require continuous nursing care
How many times have you fallen in the last 6 months? times

